1.6 Study Variables

A. Primary Outcome:

Viral load at 10 days post randomization

B. Other measures

Age, Gender Race/ethnicity BMI Co-morbidity:

- Diabetes mellitus
- Hypertension
- Chronic bronchitis, emphysema, or chronic obstructive pulmonary disease (COPD)
- Other lung disease
- Coronary artery disease, peripheral artery disease, angina, or heart attack (myocardial infarction)
- Congestive heart failure
- Stroke or transient ischemic attack (TIA)
- Atrial fibrillation
- Cancer other than non-melanoma skin cancer
- Chronic kidney disease (CKD)
- Crohn's disease, ulcerative colitis, or inflammatory bowel disease (IBD)
- Rheumatoid arthritis (RA), psoriasis, systemic lupus, multiple sclerosis, or another autoimmune disorder
- Allergic rhinitis

Medications Symptoms Household infection (confirmed or suspected)

List variables of interest

Treatment Variables:

- Treatment Compliance
- Adverse Events (number/percentage/grade)

1.7 Drugs/Devices/Biologics

Generic name: Hydroxychloroquine sulfate

[figure not shown]
Commercial name: Plaquenil

For complete information please refer to the package inserts at http://dailymed.nlm.nih.gov/dailymed/Hydroxychloroquine

Chemical name: 7-Chloro-4-[4-[ethyl-(2-hydroxyethyl) amino]-1-methylbutylamino] quinolone

Source: Commercially available

C18H26CIN3O•H2SO4

Molecular Weight: 433.95

Hydroxychloroquine sulfate tablets, USP contain 200 mg hydroxychloroquine sulfate, equivalent to 155 mg base, and are for oral administration.

Pharmacokinetics: Following a single 200 mg oral dose of hydroxychloroquine sulfate to healthy males, the mean peak blood concentration of hydroxychloroquine was 129.6 ng/mL, reached in 3.26 hours with a half-life of 537 hours (22.4 days). In the same study, the plasma peak concentration was 50.3 ng/mL reached in 3.74 hours with a half-life of 2963 hours (123.5 days). Urine hydroxychloroquine levels were still detectable after 3 months with approximately 10% of the dose excreted as the parent drug. Results following a single dose of a 200 mg tablet versus I.V. infusion (155 mg), demonstrated a half-life of about 40 days and a large volume of distribution.

Mechanism of Action: The precise mechanism by which hydroxychloroquine exhibits activity against *Plasmodium* is not known. Hydroxychloroquine, like chloroquine, is a weak base and may exert its effect by concentrating in the acid vesicles of the parasite and by inhibiting polymerization of heme. It can also inhibit certain enzymes by its interaction with DNA.

Warnings:

Ocular: Irreversible retinal damage has been observed in some patients who had received hydroxychloroquine sulfate. Significant risk factors for retinal damage include daily doses of hydroxychloroquine sulfate greater than 6.5 mg/kg (5 mg/kg base) of actual body weight, durations of use greater than five years, subnormal glomerular filtration, use of some concomitant drug products such as tamoxifen citrate and concurrent macular disease.

Cardiac Effects, including Cardiomyopathy and QT prolongation: Post-marketing cases of life-threatening and fatal cardiomyopathy have been reported with use of hydroxychloroquine sulfate as well as with use of chloroquine. Hydroxychloroquine sulfate prolongs the QT interval. Ventricular arrhythmias and torsades de pointes have been reported in patients taking hydroxychloroquine sulfate (see OVERDOSAGE). Therefore, hydroxychloroquine sulfate should not be administered with other drugs that have the potential to prolong the QT interval.

Worsening of psoriasis and porphyria

Proximal Myopathy and Neuropathy

Neuropsychiatric events, including suicidality

Hypoglycemia: Hydroxychloroquine sulfate has been shown to cause severe hypoglycemia including loss of consciousness that could be life threatening in patients treated with or without antidiabetic medications

General precautions: General: Use with caution in patients with gastrointestinal, neurological, or blood disorders, and in those with a sensitivity to quinine.

Hepatic/Renal Disease: Antimalarial compounds should be used with caution in patients with hepatic disease or alcoholism or in conjunction with known hepatotoxic drugs. A reduction in dosage may be necessary in patients with hepatic or renal disease, as well as in those taking medicines known to affect these organs.

Hematologic Effects/Laboratory Tests: Antimalarial compounds should be used with caution in patients with hepatic disease or alcoholism or in conjunction with known hepatotoxic drugs. Periodic blood cell counts should be performed if patients are given prolonged therapy.

Hydroxychloroquine sulfate should be administered with caution in patients having glucose-6-phosphate dehydrogenase (G-6-PD) deficiency.

Dermatologic Effects: Dermatologic reactions to hydroxychloroquine sulfate may occur and, therefore, proper care should be exercised when it is administered to any patient receiving a drug with a significant tendency to produce dermatitis.

Drug Interactions (include but not limited to): Digoxin, Insulin or antidiabetic drugs, Drugs that prolong QT interval and other arrhythmogenic drugs, Mefloquine and other drugs known to lower the convulsive threshold, Antiepileptics, Methotrexate, Cyclosporin, Praziquantel, Antacids and kaolin, Cimetidine, Ampicillin.

Availability: FDA approved; commercially available hydroxychloroquine sulfate will be supplied free of charge to all patients enrolled.

[figure not shown]
Generic name: Ribavirin Commercial name:

For complete information please refer to the package inserts at http://dailymed.nlm.nih.gov/dailymed/ribavirin

Chemical name: 1-β-Dribofuranosyl-1H-1,2,4-triazole-3-carboxamide

Source: Commercially available

 $C_8 H_{12} N_4 O_5$ and the molecular weight is 244.2

Ribavirin, USP is white, crystalline powder. It is freely soluble in water and slightly soluble in dehydrated alcohol. Each film-coated ribavirin tablet intended for oral administration contains 200 mg or 400 mg or 500 mg or 600 mg of ribavirin. In addition, each tablet contains the following inactive ingredients: crospovidone, hypromellose, iron oxide red, iron oxide yellow, magnesium stearate, microcrystalline cellulose, polyethylene glycol, povidone, silicon dioxide, talc, and titanium dioxide.

Pharmacokinetics

Multiple dose ribavirin pharmacokinetic data are available for HCV patients who received ribavirin in combination with peginterferon alfa-2a. Following administration of 1200 mg/day with food for 12 weeks mean±SD (n=39; body weight greater than 75 kg) AUC was 25,361±7110 ng·hr/mL and C was 2748±818 ng/mL. The average time to reach C was 2 hours. Trough ribavirin plasma concentrations following 12 weeks of dosing with food were 1662±545 ng/mL in HCV infected patients who received 800 mg/day (n=89), and 2112±810 ng/mL in patients who received 1200 mg/day (n=75; body weight greater than 75 kg). The terminal half-life of ribavirin following administration of a single oral dose of ribavirin is about 120 to 170 hours. The total apparent clearance following administration of a single oral dose of ribavirin is about 26 L/h. There is extensive accumulation of ribavirin after multiple dosing (twice daily) such that the C at steady state was four-fold higher than that of a single dose.

Contraindications:

Ribavirin

Pregnancy: Women who are or may become pregnant. Ribavirin may cause fetal harm when administered to a pregnant woman. women who are or may become pregnant. If this drug is used during pregnancy, or if the patient becomes pregnant while taking this drug, the patient should be apprised of the potential hazard to the fetus Men whose female partners are pregnant.

Hemoglobinopathies: Patients with hemoglobinopathies (e.g., thalassemia major or sickle-cell anemia).

Protocol Title: A Triple Combination Antiviral Coronavirus Therapy (TriACT) RCT Protocol Version Date: V3.2 8Oct2020

In combination with didanosine: Reports of fatal hepatic failure, as well as peripheral neuropathy, pancreatitis, and symptomatic hyperlactatemia/lactic acidosis have been reported in clinical trials.

Ribavirin and peginterferon alfa-2a combination therapy is contraindicated in patients with:

Autoimmune hepatitis.

Hepatic decompensation (Child-Pugh score greater than 6; class B and C) in cirrhotic CHC mono infected patients before treatment.

Hepatic decompensation (Child-Pugh score greater than or equal to 6) in cirrhotic CHC patients coinfected with HIV before treatment.

Warnings:

Significant adverse reactions associated with ribavirin/peginterferon alfa-2a combination therapy include severe depression and suicidal ideation, hemolytic anemia, suppression of bone marrow function, autoimmune and infectious disorders, ophthalmologic disorders, cerebrovascular disorders, pulmonary dysfunction, colitis, pancreatitis, and diabetes. The Peginterferon alfa-2a Package Insert should be reviewed in its entirety for additional safety information prior to initiation of combination treatment.

Pregnancy

Ribavirin may cause birth defects and/or death of the exposed fetus. Ribavirin has demonstrated significant teratogenic and/or embryocidal effects in all animal species in which adequate studies have been conducted. These effects occurred at doses as low as one twentieth of the recommended human dose of ribavirin. Ribavirin therapy should not be started unless a report of a negative pregnancy test has been obtained immediately prior to planned initiation of therapy.

Anemia

The primary toxicity of ribavirin is hemolytic anemia, which was observed in approximately 13% of all ribavirin/peginterferon alfa-2a- treated participants in clinical trials. Anemia associated with ribavirin occurs within 1 to 2 weeks of initiation of therapy. Because the initial drop in hemoglobin may be significant, it is advised that hemoglobin or hematocrit be obtained pretreatment and at week 2 and week 4 of therapy or more frequently if clinically indicated. Patients should then be followed as clinically appropriate. Caution should be exercised in initiating treatment in any patient with baseline risk of severe anemia (e.g., spherocytosis, history of gastrointestinal bleeding). Fatal and nonfatal myocardial infarctions have been reported in patients with anemia caused by ribavirin. Patients should be assessed for underlying cardiac disease before initiation of ribavirin therapy. Patients with pre-existing cardiac disease should have electrocardiograms administered before treatment and should be appropriately monitored during therapy. If there is any deterioration of cardiovascular status, therapy should be suspended or discontinued. Because cardiac disease may be worsened by drug-induced anemia, patients with a history of significant or unstable cardiac disease should not use ribavirin.

Hepatic Failure

Chronic hepatitis C (CHC) patients with cirrhosis may be at risk of hepatic decompensation and death when treated with alpha interferons, including peginterferon alfa-2a. Cirrhotic CHC patients coinfected with HIV receiving highly active antiretroviral therapy (HAART) and interferon alfa-2a with or without ribavirin appear to be at increased risk for the development of hepatic decompensation compared to patients not receiving HAART.

Hypersensitivity

Severe acute hypersensitivity reactions (e.g., urticaria, angioedema, bronchoconstriction, and

anaphylaxis) have been observed during alpha interferon and ribavirin therapy. If such a reaction occurs, therapy with peginterferon alfa-2a and ribavirin should be discontinued immediately, and appropriate medical therapy instituted. Serious skin reactions including vesiculobullous eruptions, reactions in the spectrum of Stevens-Johnson Syndrome (erythema multiforme major) with varying degrees of skin and mucosal involvement and exfoliative dermatitis (erythroderma) have been reported in patients receiving peginterferon alfa-2a with and without ribavirin. Patients developing signs or symptoms of severe skin reactions must discontinue therapy

Pulmonary Disorders

Dyspnea, pulmonary infiltrates, pneumonitis, pulmonary hypertension, and pneumonia have been reported during therapy with ribavirin and interferon. Occasional cases of fatal pneumonia have occurred. In addition, sarcoidosis or the exacerbation of sarcoidosis has been reported. If there is evidence of pulmonary infiltrates or pulmonary function impairment, patients should be closely monitored and, if appropriate, combination ribavirin/peginterferon alfa-2a treatment should be discontinued.

Bone Marrow Suppression

Pancytopenia (marked decreases in RBCs, neutrophils, and platelets) and bone marrow suppression have been reported in the literature to occur within 3 to 7 weeks after the concomitant administration of pegylated interferon/ribavirin and azathioprine. In this limited number of patients (n=8), myelotoxicity was reversible within 4 to 6 weeks upon withdrawal of both HCV antiviral therapy and concomitant azathioprine and did not recur upon reintroduction of either treatment alone. peginterferon alfa-2a, ribavirin, and azathioprine should be discontinued for pancytopenia, and pegylated interferon/ribavirin should not be re-introduced with concomitant azathioprine.

Pancreatitis

Ribavirin and peginterferon alfa-2a therapy should be suspended in patients with signs and symptoms of pancreatitis and discontinued in patients with confirmed pancreatitis.

Impact on Growth in Pediatric Patients

During combination therapy for up to 48 weeks with peginterferon alfa-2a plus ribavirin, growth inhibition was observed in pediatric participants 5 to 17 years of age. Decreases in weight for age z-score and height for age z-score up to 48 weeks of therapy compared with baseline were observed. At 2years post-treatment, 16% of pediatric participants were more than 15 percentiles below their baseline weight curve and 11% were more than 15 percentiles below their baseline height curve. The available longer term data on participants who were followed up to 6 years post-treatment are too limited to determine the risk of reduced adult height in some patients [see Clinical Studies Experience

Drug interactions: Didanosine, zidovudine

Availability: FDA approved; commercially available Ribavirin will be supplied free of charge to all patients enrolled.

[figure not shown]
Generic name: Nitazoxanide Commercial name: ALINIA

For complete information please refer to the package inserts at http://dailymed.nlm.nih.gov/dailymed/nitazoxanide

Chemical name: 2-acetyloxy- N-(5-nitro-2-thiazolyl) benzamide

Source: Commercially available

 C_{12} H₉ N₃ O₅ S and the molecular weight is 307.3

Nitazoxanide is a light yellow crystalline powder. It is poorly soluble in ethanol and practically insoluble in water.

ALINIA Tablets contain 500 mg of nitazoxanide and the following inactive ingredients: maize starch, pregelatinized corn starch, hydroxypropyl methylcellulose, sucrose, sodium starch glycollate, talc, magnesium stearate, soy lecithin, polyvinyl alcohol, xanthan gum, titanium dioxide, D&C Yellow No. 10 Aluminum Lake, FD&C Yellow No. 6 Aluminum Lake, and FD&C Blue No. 2 Aluminum Lake.

ALINIA for Oral Suspension, when reconstituted with 48 mL of water, produces 60 mL of a homogeneous suspension with a pink color that contains 100 mg nitazoxanide per 5 mL and the following inactive ingredients: sodium benzoate, sucrose, xanthan gum, microcrystalline cellulose and carboxymethylcellulose sodium, anhydrous citric acid, sodium citrate dihydrate, maltodextrin, modified food starch, triacetin, FD&C Red No. 40 and artificial strawberry flavoring.

Pharmacokinetics

Absorption Single Dosing: Following oral administration of ALINIA Tablets or Oral Suspension, the parent drug, nitazoxanide, is not detected in plasma.

Multiple dosing: Following oral administration of a single ALINIA Tablet every 12 hours for 7 consecutive days, there was no significant accumulation of nitazoxanide metabolites tizoxanide or tizoxanide glucuronide detected in plasma.

Bioavailability: ALINIA for Oral Suspension is not bioequivalent to ALINIA Tablets. The relative bioavailability of the suspension compared to the tablet was 70%. When ALINIA Tablets are administered with food, the AUC of tizoxanide and tizoxanide glucuronide in plasma is increased almost two-fold and the C_{max} is increased by almost 50%. When ALINIA for Oral Suspension was administered with food, the AUC of tizoxanide glucuronide increased by about 45-50% and the C_{max} increased by $\leq 10\%$.

Distribution: In plasma, more than 99% of tizoxanide is bound to proteins.

Elimination Metabolism: Following oral administration in humans, nitazoxanide is rapidly hydrolyzed to an active metabolite, tizoxanide (desacetyl-nitazoxanide). Tizoxanide then undergoes conjugation, primarily by glucuronidation.

Excretion: Tizoxanide is excreted in the urine, bile, and feces, and tizoxanide glucuronide is excreted in urine and bile. Approximately two-thirds of the oral dose of nitazoxanide is excreted in the feces and one-third in the urine.

Contraindications:

Hypersensitivity: ALINIA Tablets and ALINIA for Oral Suspension are contraindicated in patients with a prior hypersensitivity to nitazoxanide or any other ingredient in the formulations.

Drug interactions: Highly Protein Bound Drugs with Narrow Therapeutic Indices i.e. Tizoxanide, warfarin

Availability: FDA approved; commercially available Ribavirin will be supplied free of charge to all patients enrolled.

There is no current data that assess the risks of the use of all three drugs in combination.

A. Drug/Device Accountability and Storage Methods

Drug accountability logs and pharmacy records must be maintained at each pharmacy location and must be available for review upon request. Drug accountability logs and pharmacy records will be reviewed during monitoring visits and by the Research Pharmacist

B. Treatment Compliance

The study medication will be given in accordance with the protocol and the instructions of the treating investigator. The study drugs will be provided to participants to be self-administered. Participants will be asked to confirm medication dosing each day on daily logs and on the day 3 and day 6 call with research staff.

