1.3 Research Design and Methods

We will conduct a randomized clinical trial enrolling eligible participants who are determined to be SARS-CoV-2-positive (e.g., via Rutgers Corona Cohort [RCC] study, hospital or other screening programs) who volunteer for the study. Specifically, we will enroll 70 participants whose test has been performed within the past 7 days who are either asymptomatic or mildly symptomatic at baseline. Mild COVID-19 symptoms include new cough, sore throat, fever, myalgias, new vomiting or diarrheaor change in smell or taste. Illness requiring hospitalization, or those who present with hypoxia (PO2<92%) or shortness of breath at time of enrollment will be classified as significantly symptomatic and excluded from study participation. People who are allergic or intolerant to NTZ, RBV or HCQ will be excluded. We will randomly allocate participants stratified by presence of mild symptoms to 1) NTZ, RBV and HCQ or 2) placebo. Treatment with the investigational agents or placebo will continue for 5 days. Viral load will be assessed at baseline (day 0) as well as at days 3, 6, and 10 to monitor response to antiviral treatment. Immune status will be determined by antibody testing of blood collected at baseline and day 28.

Prior to initiating enrollment, we will prepare two randomization tables for treatment assignment using permuted blocks of six which will be provided to the research pharmacist. One table will be used for participants without symptoms and the other will be used for those with mild symptoms. The pharmacist will prepare kits containing the 5-day supply of study medications (investigational drugs/placebo) which will be sequentially numbered in accordance with the randomization tables. The contents of each kit (investigation drugs/placebo) will be indistinguishable. Study staff will establish symptom status at the baseline visit, and per pharmacy order, provide the participant the next numbered medication kit in the participant's stratum (no symptoms/mild symptoms). The study investigators, staff interacting with the participants are all masked to treatment assignment

A. Research Procedures

- 1. Study Procedures:
 - Day 0/1 Screening/Baseline Visit (in person)
 - Pre-screen via online screening form to confirm eligibility
 - Obtain informed consent for trial enrollment
 - Medical history
 - Medication history
 - Document symptoms (if any)

- o Take temperature, PO2, Pulse
- Q-T interval assessment

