- Obtain urine pregnancy test for females of childbearing potential
- Collect research specimens: mid-turbinate nasal swab and blood for CBC, chem profile and immune status
- Randomize study participant
- Dispense study medication
- Provide Zio AT ECG monitoring device for ongoing Q-T interval assessment
- Provide thermometer and pulse oximeter and home collection kits and provide education on use
- Provide education to participant on how to complete temperature log and confirm medication self-dosing and self-collection of mid-turbinate swab.
- Study participant doses self with prescribed study medications the same day if instructed by the study staff

• Days 1-5 – Treatment Period (phone /online)

- Study participant doses self with prescribed study medications days 1 to 5
- Self-collecting of mid-turbinate swab day 3
- Questionnaire completed by participant daily day 1-day 5
- Temperature, PO2, and pulse
- o Day 3 telephone call procedure review and confirm self- specimen collection/AEs
- Days 6- 10
 - Questionnaire completed by participant days 6 to10
 - Self-collecting of mid-turbinate swab days 6 and 10
 - Temperature, PO2 and pulse
 - Day 6 and 10 telephone call procedure review and confirm self-specimen collection/AEs
- Day 14- Follow-up (in person)
 - In person visit to draw blood sample for CBC and chem panel
 - o Return Zio AT ECG monitoring device
- Day 28 Follow-up (in person)
 - In person visit to draw blood sample for CBC, chem panel, and immune function at 28 days
 - Obtain urine pregnancy test for females of childbearing potential
 - o Questionnaire completed by participant
 - o Final AE assessment

Study Flow/Schedule of Events:

Procedure	Pre- Screen -5 days	Screening /Baseline (Day 0/1)	Daily x 5 days	Days 6 to 10	Days 3, 6, 10	Day 14 (Office)	Day 28 +/- 4 (Office)
Pre-screen questionnaire	Х						
Consent		Х					
Baseline questionnaire (inc. Medical History)		X					
Q-T Interval		Х	Х	Х			
Self administered Symptom questionnaire		Х	Х	X			Х
Drug accountability (Treatment compliance)		Х	Х				X
Temperature		Х	Х	х			
PO2 and Pulse		Х	Х	х			
Urine Pregnancy Test		Х					Х
CBC w/ diff/platelet		Х				Х	Х
Comprehensive metabolic panel		Х				Х	Х
Mid-turbinate self nasal swab for viral shedding		Х			Х		
Blood test for immune function		X					Х
Study medication		X (if day1)	X (BID)				
Telephone Follow-up procedure review & confirm self- specimen collection/					X		
AE Review					х		x

- 2. Treatment Plan:
 - Dosage and Administration

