Non-serious adverse events and SAEs will be determined from the time the study drug is given, throughout the treatment period and up to and including the one month follow-up period. All grade 3 or higher AEs will be recorded. Grade 1 - 2 AEs do not need to be recorded. After withdrawal from treatment, participants must be followed-up for all existing and new AEs for 60 calendar days after the last dose of trial drug and/or until event resolution. All new AEs occurring during that period must be recorded (if SAEs, they must be reported to Data Safety Monitoring Board (DSMB) and Rutgers IRB as per SOPs.).

All study-related toxicities/ SAEs must be followed until resolution, unless in the Treating Investigator's opinion, the condition is unlikely to resolve due to the patient's underlying disease.

3. Reporting of Serious Adverse Events

Investigators and other site personnel must inform the DSMB and Rutgers IRB. FDA will be informed as required accordance with the reporting obligations of 21 CFR 312.32. It is the responsibility of the principal investigator to compile all necessary information and ensure that the FDA receives a report according to the FDA reporting requirement timelines.

All SAEs meeting the criteria for expedited reporting will be reported to the Rutgers IRB within the mandated time frames. All SAEs within the safety follow-up window (e.g., within 30 days after the last dose of study medications) established in the protocol will be reported.

- 4. Clinical Safety Assessments
 - Recording of Adverse Events

Non-serious adverse events and SAEs will be determined from the time the study drug is given, throughout the treatment period and up to and including the 28-day follow-up period. All grade 3 or higher AEs will be recorded. Grade 1-2 AEs do not need to be recorded. After withdrawal from treatment, participants must be followed-up for all existing and new AEs for 28 calendar days after the last dose of trial drug and/or until event resolution. All new AEs occurring during that period must be recorded (if SAEs, they must be reported to the Data Safety Monitoring Committee and Rutgers IRB).

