Uncommon: ≥ 0.1 and < 1 %: Maculopathies, which may be irreversible. Retinopathy with changes in pigmentation and visual field defects (see Warnings and Precautions, Ophthalmologic). In its early form it appears reversible upon discontinuation of the drug. If allowed to develop however, there may be a risk of progression even after treatment withdrawal. Patients with retinal changes may be asymptomatic initially, or may have scotomatous vision with paracentral, pericentral ring types, temporal scotomas, abnormal color visions, reduction in visual acuity, night blindness, difficulty reading and skipping words. Corneal changes including edema and opacities. They are either symptomless or may cause disturbances such as halos around lights especially at night, blurring of vision, vision disturbances, or photophobia. They may be transient or are reversible upon discontinuation of therapy (see Warnings and Precautions, Ophthalmologic). *Not known*: Macular degeneration, which may be irreversible.

Gastrointestinal disorders

Very common: \geq 10 %: Abdominal pain, nausea. Common: Diarrhea, vomiting. These symptoms usually resolve immediately upon reducing the dose or upon stopping the treatment.

• Hepatobiliary disorders

Uncommon: ≥ 0.1 and < 1 %: Abnormal liver function tests. Not known: Fulminant hepatic failure (see Warnings and Precautions, Hepatic/Biliary/Pancreatic).

Immune system disorders

Not known: Urticaria, angioedema, bronchospasm.

• Metabolism and nutrition disorders

Common: \geq 1 and <10 %: Anorexia (usually resolves immediately upon reducing the dose or upon stopping the treatment). Not known: hypoglycemia (see Warnings and Precautions, Endocrine and Metabolism). Hydroxychloroquine may exacerbate porphyria (see Warnings and Precautions, General).

• Musculoskeletal and connective tissue disorders

Uncommon: ≥ 0.1 and < 1 %: Sensori motor disorders. Not known: Skeletal muscle palsies or skeletal muscle myopathy or neuromyopathy leading to progressive weakness and atrophy of proximal muscle groups. Depression of tendon reflexes, abnormal results of nerve conduction tests. Myopathy may be reversible after drug discontinuation, but recovery may take many months (see Warnings and Precautions, Musculoskeletal).

• Nervous system disorders

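### Hydroxychloroquine hypoglycemia is a named risk, yet antidiabetic users can be dosed at home with no stated precaution, and milder episodes need not be recorded as adverse events

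*Combined protocol and SAP*

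**What the plan says.** The hydroxychloroquine warnings in section 1.7 state: "Hydroxychloroquine sulfate has been shown to cause severe hypoglycemia including loss of consciousness that could be life threatening". The same sentence says this applies with or without antidiabetic treatment. The interaction list in 1.7 names "Insulin or antidiabetic drugs" and attaches no instruction. Section 4.7 A lists hypoglycemia again among metabolic disorders, with frequency not known. Further on, 4.7 A has an entry for harm to a participant with an existing condition, and it is marked not applicable.

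The information needed to identify people at higher risk is already collected. The baseline visit in section 1.3 A.1 includes "Medication history", which comes before "Randomize study participant" in the list of steps. Section 1.6 B lists "Diabetes mellitus" as a recorded co-morbidity.

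On recording, section 1.3 C.2 requires grade 3 or higher adverse events to be recorded and adds: "Grade 1 - 2 AEs do not need to be recorded". Section 1.3 C.4 repeats the rule.

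**The concern.** The plan names a hazard that can be life threatening and a class of drugs that interacts with it, then sets no step for people who take those drugs. Treatment is self-administered at home, so nobody is on hand if an episode occurs. The first stake is patient safety: people at identifiable risk may start dosing without anyone having considered it.

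The second stake is what the trial learns. Section 1.4 says there is no previous human experience with this combination. Secondary objective 6 compares side effects, section 1.6 lists adverse events by number, percentage and grade, and under section 6.3 B the monitoring board reviews reported adverse events once half the participants are enrolled. A milder hypoglycemic episode during dosing need not reach any of these.

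**Working it through.** The plan gives no figure on this point to reproduce. The check is to look at each place where a precaution or a record would sit.

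1. **Eligibility (4.1 C).** Diabetes is not an exclusion. Exclusion 7 has 15 drug entries, of which 0 are antidiabetics. This count says little by itself, because the list is essentially QT-related drugs plus tamoxifen.
2. **Concomitant medication (1.3 A.2).** It covers supportive care and antipyretics. It says nothing on glucose checks or antidiabetic dosing.
3. **Minimizing risks (4.7 E).** It covers QTc and arrhythmia, and hemolytic anemia. It adds a metabolic panel with no glucose threshold or action.
4. **Timing of that panel.** Draws are at baseline, day 14 and day 28, and dosing runs over days 1 to 5. The first draw after baseline is therefore 14 − 5 = 9 days after the last dosing day. The analytes are not listed; that glucose is among them is an assumption.
5. **Recording (1.3 C.2 and C.4).** Both statements waive grade 1-2 events. Both also say that all new adverse events after withdrawal from treatment must be recorded. That sits uneasily with the waiver, but it does not clearly cover the dosing days. No grading scale is named, so the glucose value at which recording becomes mandatory cannot be fixed from the text.
6. **Other channels.** Section 1.9 A describes daily questions on reactions to study medication through day 10, and section 1.3 A.1 has adverse event calls on days 3, 6 and 10. No text turns a mild report from these into an adverse event record.

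**Number of people concerned.** Reviews = 70 × share using an antidiabetic. The plan gives no share, so a range is assumed.

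| Assumed share | Of 70 enrolled | Of 35 on active treatment |
|---|---|---|
| 2% | 1.4 | 0.7 |
| 5% | 3.5 | 1.75 |
| 10% | 7 | 3.5 |
| 15% | 10.5 | 5.25 |

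**What a table by arm could show.** Suppose all events fall in the active arm, with 35 analyzed per arm. The two-sided Fisher p-value for k events against 0 is 2 × C(35,k)/C(70,k).
- k = 5: 2 × 324,632/12,103,014 = 0.054.
- k = 6: 2 × 1,623,160/131,115,985 = 0.025.

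It would take a split of 6 to 0 to cross the 5% level. With the handful of antidiabetic users in the table above, a comparison of arms would say almost nothing. The case for recording is therefore individual safety and description.

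**The case against.** The strongest reply is that hypoglycemia is only one label warning among many. In the same part of section 1.7, the cautions on psoriasis and porphyria, myopathy, neuropsychiatric events and hepatic disease also led to no exclusion. Of the 11 interaction entries, only QT-prolonging and arrhythmogenic drugs became exclusions; the other 10 did not. This stands. A reader who sees that retinal disease, G-6-PD deficiency and tamoxifen are screened for might infer that hypoglycemia was singled out for neglect. The documents do not support that, and no such contrast is claimed here.

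Second, the warning concerns severe episodes, and those are captured as grade 3 or higher events or as serious adverse events. This also stands, and it limits the recording gap to milder episodes. It does not answer the lack of a precaution before dosing.

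Third, there are partial safeguards: doses are taken with a meal or milk, drug reactions are asked about daily, and there are three adverse event calls. The metabolic panel at day 14 is not irrelevant either, since the stated blood half-life of hydroxychloroquine is 22.4 days and exposure continues after dosing. These reduce the concern. None of them is tied to glucose or to antidiabetic use.

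Fourth, the consent form and the questionnaire items are not available to read, and either may contain counseling or a relevant question. So it cannot be said that participants receive no advice, only that the protocol text states none. The reference in 1.7 to the package insert is not a protocol procedure.

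**Conclusion.** The point holds as a minor, inexpensive safety improvement. The plan names the hazard and the interacting drugs, collects the data that identify the people concerned, and states no action for them. Both adverse event rules allow milder episodes to go unrecorded as adverse events.

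Three stronger readings should be resisted. A reader might infer that life-threatening hypoglycemia would be missed; it would not, under the rules for grade 3 or higher and serious events. A reader might infer that diabetes ought to be an exclusion; the plan gives the frequency as not known and offers no basis for that. A reader might infer that secondary objective 6 is compromised; with 35 per arm, mild hypoglycemia could hardly support a comparison however it was recorded.

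The number of people concerned rests entirely on the assumed 2% to 15% antidiabetic use. No event rate is estimated. The primary analysis, alpha and power are unaffected.

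**What to change.** 1. **Baseline (1.3 A.1), after the medication history and before randomization.** For a participant on insulin or another antidiabetic, the investigator reviews and documents whether to proceed. If so, advise on hypoglycemia symptoms and on glucose checks with a meter the participant already owns. Tell all participants the symptoms, because the warning applies with or without antidiabetics. Placing this before randomization avoids anyone being randomized and then not dosed.
2. **Calls.** Ask about hypoglycemia at the existing adverse event calls on days 3, 6 and 10.
3. **Recording.** Amend both 1.3 C.2 and 1.3 C.4 so that hypoglycemia is an exception to the waiver and is recorded at any grade. State the glucose cut-off in the protocol. List the reports descriptively, with symptom-only and glucose-confirmed episodes shown separately, and claim no meaningful comparison between arms. Meter owners will mostly be people with diabetes, so confirmed episodes will be found more readily in them; the listing should say so.

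**Cost.** 1.4 to 10.5 investigator reviews under the assumed range; 3 × 70 = 210 extra questions on calls already planned; one clause in two places; some nonspecific symptom reports from acutely infected people; and possibly a few volunteers not enrolled.
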